Recent advances in regenerative medicine have introduced novel treatment modalities, including bioengineered skin substitutes and biological matrices, which have shown promise in accelerating wound healing and improving clinical outcomes [7]. Among these, high-purity type-I collagen- based skin substitutes (HPTC) and dehydrated human amnion/chorion membrane (dHACM) have emerged as promising therapeutic options [8, 9]. Type-I collagen, comprising 97% structural similarity across species, provides an optimal scaffold for cellular attachment and tissue regeneration [10]. This bioengineered collagen matrix mimics the native extracellular architecture and creates a conducive microenvironment for cell migration, proliferation, and differentiation. The inherent non-immunogenic properties of highly purified type-I collagen, which are attributed to the absence of sulphur-containing amino acids that typically trigger immune responses, make it particularly suitable and well-tolerated for wound healing applications [11].

Conversely, dHACM utilizes the natural regenerative properties of placental membranes, which have been employed clinically for over a century [12]. The amnion and chorion membranes contain growth factors, cytokines, and extracellular matrix components that facilitate wound healing through anti-inflammatory and pro-regenerative mechanisms [13].

However, processing methods may affect the bioactivity of these products, potentially limiting their therapeutic efficacy [14].

Previous single-centre studies have suggested potential advantages of HPTC over dHACM in treating chronic wounds [15, 16]. However, the evidence base remains limited, with small sample sizes and single-centre designs limiting the generalizability of findings. Furthermore, most comparative studies lack comprehensive histological analysis to elucidate the underlying mechanisms of action.

The objective of this multicentre randomized controlled trial was to compare the safety and efficacy of HPTC versus dHACM in treating DFUs, with particular emphasis on wound healing kinetics, histological parameters, and patient-centred outcomes. We desire to reiterate our previous single centre study result [17], that HPTC would demonstrate superior wound healing outcomes through enhanced cellular activity and improved tissue regeneration.

MATERIALS AND METHODS

Study Design and Setting

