osteomyelitis or exposed bone in the wound bed, current use of immunosuppressive therapy, diagnosis of active malignancy, pregnancy or lactation, end-stage renal disease requiring dialysis, acute Charcot foot deformity, previous amputation that would affect target ulcer offloading capacity, and participation in other investigational studies within the preceding 30 days.

Randomization and Blinding

Eligible patients were randomized 1:1 using computer-generated random sequence with variable block sizes (4, 6, 8) stratified by site. Allocation concealment was maintained using sequentially numbered opaque sealed envelopes. Due to the nature of the interventions, participants and investigators could not be blinded to treatment allocation. However, outcome assessors for wound parameters (photograph-based planimetry was performed by a central reader), histological analysis and quality of life measurements were blinded to treatment assignment.

Interventions

All participants received standardized wound care including debridement, infection control, glycaemic optimization, and pressure offloading using total contact casting or removable cast walkers. Subjects who met the study's inclusion criteria after the screening period were randomized into one of two groups:

- a. The HPTC arm (n=60) received high-purity type-I collagen-based skin substitute (Helicoll®, Encoll Corp, USA) that was carefully trimmed to precisely cover the wound bed, followed by application of standard of care (SOC) wound dressing. The reapplication schedule for HPTC was determined by the treating investigator's clinical judgment based on wound assessment and healing progress.
- b. The dHACM group (n=60) received dehydrated human amnion/chorion membrane applied according to manufacturer instructions with concurrent application of standard of care (SOC), with repeat applications performed as clinically indicated based on wound healing response.

During the four-week treatment phase, patients were re-evaluated on days 7, 14, 21, and 28. The SOC bandage in both groups included an identical three-layer dressing systems: non-adherent paraffin gauze (primary layer), absorbent gauze pads (secondary layer), and soft roll with crepe bandage (tertiary layer) - standardized 3-layer dressing system.

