- c. fibroblast activity quantified on a 0-3 scale based on α -SMA positive fibroblast count and cellular morphology,
- d. capillary density measured as vessels per mm^2 using CD31 immunohistochemical staining,
- e. inflammatory response graded on a 0-3 semi-quantitative scale, and
- f. collagen deposition assessed on a 0-3 scale using Masson's Trichrome staining.

Additional secondary outcomes included

2. Time to complete wound closure defined as 100% re-epithelialization with no drainage,
3. Percentage wound area reduction measured weekly using standardized digital photography,
4. Mean number of treatment applications representing the total applications required per participant during the 4-week treatment period,
5. Adverse events including infection and other complications monitored throughout the study period,
6. Quality of life assessed using patient-reported visual analogue scale (VAS) measuring change from baseline to follow-up week, and
7. Scar quality evaluated using the Vancouver Scar Scale at 5 weeks post-treatment

Vascularity assessment was done using biopsy on day zero of application to be compared with day five after the application of HPTC or dHCAM. For histopathological assessment, before application and on the fifth day after the application of either HPTC or dHCAM, a 2 mm punch biopsy was obtained from the wound edge extending into the wound bed under local anaesthesia (2% lidocaine without epinephrine). Biopsy samples were immediately fixed in 10% neutral buffered formalin for 24 hours, processed through graded alcohol, and embedded in paraffin blocks. Serial sections of 4 μm thickness were prepared and stained with hematoxylin and eosin (H&E) for general morphology, Masson's trichrome for collagen assessment, CD31 immunohistochemistry for capillary density evaluation, and α -SMA immunohistochemistry for fibroblast activity. Histological parameters that were evaluated included vascular infiltration, neo-epithelialization, fibroblast activity, capillary density,

inflammatory response, and collagen deposition (Table 1). All histological assessments were performed by two independent pathologists blinded to treatment allocation. Inter-observer agreement was assessed using Cohen's kappa coefficient.

Table 1: Histological parameters evaluated in the ulcer bed at baseline and on day five of application

Parameter	Measurement tool	Criteria	Score

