Vascular infiltration	Assessed by counting new blood vessels (0–3 scale)	Minimal vascular ingrowth (<5 vessels/HPF)	0
		Mild infiltration (5–10 vessels/HPF)	1
		Moderate infiltration (11–20 vessels/HPF)	2
		Abundant infiltration (>20 vessels/HPF)	3
Neo-epithelialization	Measured as epithelial migration distance from wound edge (0–3 scale)	No epithelial migration	0
		Minimal migration (<25% wound coverage)	1
		Moderate migration (25–75% coverage)	2
		Extensive migration (>75% coverage)	3
Fibroblast activity	Quantified by counting α -SMA positive fibroblasts per HPF and assessment of fibroblast morphology (0–3 scale)	Sparse, inactive fibroblasts	0
		Moderate cellularity, minimal matrix production	1
		High cellularity, active-matrix synthesis	2
		Very high activity with extensive matrix deposition	3
Capillary density	Evaluated using CD31 staining, counted as vessels per mm^2 of tissue		
Inflammatory response	Graded semi-quantitatively (0–3 scale)	Minimal inflammatory infiltrate	0
		Mild chronic inflammation	1
		Moderate mixed inflammation	2
		Severe acute inflammation	3
Collagen deposition	Assessed using Masson's trichrome staining (0–3 scale)	Minimal collagen matrix	0
		Loose, immature collagen	1
		Moderate organized collagen	2
		Dense, mature collagen architecture	3

*Data presented as scoring criteria; all parameters assessed using standardized histological grading scales

Sample Size Calculation

Based on previous studies, we anticipated 85% of HPTC patients and 55% of dHACM patients would achieve wound reduction. With 80% power to detect a 25% absolute difference in complete wound closure at 5 weeks, 5% significance level, and assuming 10% dropout rate, a total of n=120 with 60 participants per group were required, pooled in from across 4 centres.

Statistical Analysis

Statistical analyses were performed using SPSS version 28.0 (IBM Corp, Armonk, NY, USA) and R version 4.3.0. Continuous variables were expressed as mean \pm standard deviation or median (interquartile range) based on normality testing using Shapiro-Wilk test. Categorical variables were presented as frequencies and percentages.

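### The day-5 trichrome collagen score does not separate applied from host collagen, so residual product can be counted as deposition or, if recognised, may reveal the arm

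*Combined protocol and SAP*

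**What the plan says.** - **Product and placement.** Under Interventions, the HPTC arm receives a type-I collagen skin substitute that "was carefully trimmed to precisely cover the wound bed".
- **Sampling.** The histopathology paragraph of Outcome Measures has one biopsy before application and a second one that reaches into the bed of the ulcer: "on the fifth day after the application of either HPTC or dHCAM, a 2 mm punch biopsy was obtained from the wound edge extending into" (quote ends mid-sentence). The title of Table 1 places the histological evaluation in the ulcer bed.
- **Stain and scale.** Outcome 1f is "collagen deposition assessed on a 0-3 scale using Masson's Trichrome staining". The staining list gives "Masson's trichrome for collagen assessment" and names no method that identifies the origin of collagen. Table 1 runs from a minimal matrix (0) to "Dense, mature collagen architecture" (3).
- **Material.** The Introduction states: "Type-I collagen, comprising 97% structural similarity across species, provides an optimal scaffold for cellular attachment and tissue regeneration". It adds that the HPTC matrix resembles native extracellular architecture, and that amnion and chorion membranes also contain extracellular matrix components.
- **Readers.** "All histological assessments were performed by two independent pathologists blinded to treatment allocation". Agreement between them is measured by Cohen's kappa.

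**The concern.** The outcome is called deposition, meaning collagen the host has laid down. The scale records collagen seen in the section. In the HPTC arm the treatment is itself collagen, placed where the punch is taken. If some of it is still in the section at day 5, the score can rise without any host response.

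If a reader instead recognises the product, that reader may infer the arm. The same two pathologists grade the other subjective 0-3 items, so the blinding of those items would then also be in doubt.

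What is at stake is the mechanistic claim. The Introduction puts particular weight on histology, criticises earlier comparisons for lacking it, and expects HPTC to win through better tissue regeneration. A higher collagen score in the HPTC arm would be read as support for that, and as the scale is written it could not be told apart from the presence of the product.

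**Working it through.** The plan gives no figure for this outcome, so there is nothing to reproduce. The check has two parts.

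**1. Can the plan, as written, separate applied from host collagen?**

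| Feature of the plan | Does it separate them? |
|---|---|
| Masson's trichrome, used for collagen in general | No; no origin-specific method is listed |
| Table 1 anchors (minimal; loose and immature; moderate organised; dense and mature) | No; they grade amount and organisation |
| Day-0 biopsy | No; taken before application, so it holds no trial product to subtract |
| Two readers with Cohen's kappa | No; both can agree on the same misattribution |
| Randomisation | No; the error would follow from the assigned product |
| Scoring zone, or a rule for visible product | None stated, although fixation time and section thickness are |

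On any slide that contains product there are two routes. If the product is not distinguished from host collagen, the score may be inflated. If it is distinguished, the arm may be revealed, although the reader could also leave it out of the score. The plan handles neither.

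**2. How large could the effect on the score comparison be?**

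Inputs from the documents: 60 per arm (Sample Size Calculation); two-sided 0.05, with Mann-Whitney among the listed tests (Statistical Analysis). The plan does not say which test applies to the 0-3 scores.

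Assumptions, not in the documents: the same true score distribution in both arms; a fraction f of HPTC slides and g of dHACM slides read one grade too high, capped at 3.

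Expected shift in the mean score = (f − g) × (1 − share already at grade 3).

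- Distribution A (grades 0/1/2/3 = 25/45/25/5%), f = 30%, g = 0: 0.30 × 0.95 = 0.285.
- Distribution B (5/25/40/30%), f = 30%, g = 0: 0.30 × 0.70 = 0.21.

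Simulated two-sided rejection rates with no true difference:

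| f (HPTC) | g (dHACM) | A | B |
|---|---|---|---|
| 0 | 0 | about 5% | about 5% |
| 20% | 0 | about 20% | about 15% |
| 30% | 0 | about 40% | about 28% |
| 40% | 0 | about 64% | about 46% |
| 30% | 30% | about 5% | about 5% |
| 40% | 30% | about 9% | about 7% |

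The last two rows are the important ones: what drives false rejection is the difference in misreading between arms, not misreading as such. The choice of test matters too. Under A, a chi-square test gives about 15%, 29% and 49% at f = 20%, 30% and 40% with g = 0.

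**The case against.** The strongest reply is that exposure is not shown. Nothing in the documents says that product remains in the punch at day 5, or how much of a 2 mm sample starting at the wound edge would contain it. The similarity figure in the Introduction concerns type-I collagen as a material; it does not say that a processed product and new collagen look alike under trichrome. The comparator also brings matrix to the wound, so misreading could occur in both arms and cancel. The simulation shows what follows if there is a net bias, not that there is one. All of this stands, and it limits the point to a possibility of unknown size.

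Three stronger readings are tempting, and the documents do not support them.

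- *The bias mostly favours HPTC.* A reader might infer this because HPTC is collagen. With dHACM matrix also present and retention unknown in both arms, the net direction is not established. In the table above, every uneven row favours HPTC by assumption.
- *The pathologists were unblinded.* No section describes how either product looks under the microscope, so recognition is possible but not shown.
- *Fibroblast activity and capillary density are distorted in the same way.* Fibroblast activity rests on α-SMA-positive cell counts and morphology. Capillary density is "Evaluated using CD31 staining, counted as vessels per mm^2 of tissue"; whether product would enter that area, and whether it contains cells, is not stated.

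The reply does not remove the core. The sample is taken from where the collagen was placed, the scale ignores origin, and no listed safeguard corrects for that.

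**Conclusion.** The concern holds as a weakness of measurement validity, with a conditional threat to blinding. Collagen deposition as defined can count applied collagen as host deposition, and neither the pre-application biopsy nor reader agreement can remove that.

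The size is unknown. Under the assumptions above, false rejection runs from about 5% when misreading is equal in the two arms to between 46% and 64% for a net one-grade upgrade in 40% of HPTC slides. That range is an illustration; it rests on assumed score distributions, an assumed full-grade shift and assumed fractions.

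The scope is one of six components of a secondary outcome, plus the reliance placed on the histology blinding. The primary planimetry outcome is unaffected. The point should be dealt with before any between-arm claim about collagen deposition is made.

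**What to change.** In the histopathology paragraph of Outcome Measures and in Table 1:

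1. Score collagen deposition only in host tissue beneath or beside any visible product.
2. Have the two existing pathologists record, slide by slide, whether product is visible, and report this by arm. Repeat the comparison without those slides as a sensitivity analysis only. It selects on a feature that arises after randomisation and may differ by arm, so it cannot replace the intention-to-treat comparison.
3. Where host and applied collagen cannot be separated, report the score descriptively as collagen present, with no between-arm claim of host deposition.
4. Qualify the statement that histology was read blind according to how often product was visible.

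The cost is moderate. No new biopsies, participants or readers are needed. The document is written in the past tense, however, so existing slides may have to be re-read; some may prove unscorable for collagen, and the collagen claim becomes weaker. If little product is found in either arm, the record of that strengthens the result.

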Between-group comparisons for continuous variables used independent t-tests or Mann-Whitney U tests. Chi-square or Fisher's exact tests were employed for categorical variables. Time-to-event analysis used Kaplan-Meier curves with log-rank tests. Mixed-effects models analysed repeated measures data. All analyses followed the intention-to-treat principle, with sensitivity analyses using per-protocol populations. A two-sided p-value of less than 0.05 was considered statistically significant for all analyses, with p-values less than 0.001 indicating highly significant differences between groups.

Data collection and follow-up

Demographic data, medical history, comorbidities, and baseline wound characteristics were recorded. Laboratory parameters, including haemoglobin, albumin, and glycated haemoglobin (HbA1c), were obtained at baseline and follow-up visits.

Patients were evaluated at baseline, day 5, day 7, day 14, day 21, day 28, and day 35. At each visit, wound measurements were performed using standardized digital planimetry, with wound area calculated in cm^2 . Histopathology examination results were recorded on baseline day 0 and day 5 after application. Digital photographs were taken for documentation and independent assessment. Complete wound closure was defined as 100% epithelialization without drainage or dressing requirements. Any adverse events, if they occurred, were duly noted and notified. Scar quality and durability were assessed at each visit, with patient satisfaction assessed at the fifth week, during the one-week follow-up.

Ethical Considerations

The study was conducted in accordance with ethical principles outlined in the Declaration of Helsinki. Written informed consent was obtained from all participants before enrolment.

Participant confidentiality was maintained throughout the study period. Data safety monitoring was performed by an independent committee.

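### The Vancouver Scar Scale is a judgement-based between-arm outcome in an open-label trial, and the plan names neither its rater nor any masking

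*Combined protocol and SAP*

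**What the plan says.** The list of additional secondary outcomes ends with item 7: "Scar quality evaluated using the Vancouver Scar Scale at 5 weeks post-treatment". The item gives no rater and no masking.

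Randomization and Blinding states that "participants and investigators could not be blinded to treatment allocation". It then gives the exceptions: "outcome assessors for wound parameters (photograph-based planimetry was performed by a central reader), histological analysis and quality of life measurements were blinded". Scar quality is not among them. The only explanation of the term wound parameters is the parenthesis about planimetry. The section on histology repeats its own masking (two independent blinded pathologists). Nothing comparable is said for the scar.

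Data collection and follow-up adds that "Scar quality and durability were assessed at each visit" and that "Digital photographs were taken for documentation and independent assessment". The photographs are not linked to the scar scale, and that sentence does not mention masking.

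On analysis, "Between-group comparisons for continuous variables used independent t-tests or Mann-Whitney U tests". The Statistical Analysis section applies a two-sided 0.05 threshold to every analysis and states no multiplicity control.

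**The concern.** A scar score depends on the rater's judgement. Planimetry returns an area and cannot supply that score, so the one masked wound reading that is described does not cover the scar. As written, the scar comparison lacks the stated protection that wound area, histology and quality of life have.

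The Introduction says the investigators wish to repeat an earlier single-centre result favouring HPTC. That statement concerns wound healing rather than scars, but it puts a prior expectation on record. If the rater knew the allocation and leaned slightly towards one product, the comparison could reach p<0.05 with no difference in the scars, and the plan would call it statistically significant. At stake is a secondary claim about scar quality. The primary outcome and the sample size are not affected.

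**Working it through.** **1. Who rates the scar, and is that person masked?**

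| Outcome | Rater stated | Masking stated |
|---|---|---|
| Wound area | Central reader, from photographs | Yes |
| Histology | Two pathologists | Yes |
| Quality of life | Outcome assessors | Yes |
| Scar quality | Not stated | Not stated |

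**2. How many scars might be scored?** The plan gives no analysis set for the scar scale, so two cases are used.

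- *All randomised:* 60 per arm.
- *Closed ulcers only:* the closure rates come from the sample size section. Its 60 per arm is reproduced by 80% vs 55%, which is the stated 25-point difference over the 55% comparator rate, at two-sided 5% and 80% power:

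  n = [1.960·√(2·0.675·0.325) + 0.842·√(0.80·0.20 + 0.55·0.45)]² / 0.25² = 53.9, so 54 per arm; 54/0.9 = 60 after 10% dropout.

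  Without continuity correction, the printed 85% vs 55% gives 36, then 40 after dropout, and does not match. Taking 80% and 55% of 60 gives 0.80·60 = 48 and 0.55·60 = 33 closed ulcers, with dropout ignored.

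**3. False-positive rate under a rater shift.** Assume no true scar difference and an average rating shift of d SD towards one product. For a two-sample t-test at two-sided 0.05:

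- ncp = d·√(n₁n₂/(n₁+n₂)), df = n₁+n₂−2
- P(p<0.05) = P(|T| > t₀.₉₇₅,df), where T is noncentral t
- 48 vs 33: √(48·33/81) = 4.422, df = 79
- 60 vs 60: √(3600/120) = 5.477, df = 118

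| Assumed shift d (SD) | ncp, 48 vs 33 | P(p<0.05) | ncp, 60 vs 60 | P(p<0.05) |
|---|---|---|---|---|
| 0 | 0 | 5.0% | 0 | 5.0% |
| 0.2 | 0.884 | 14.1% | 1.095 | 19.2% |
| 0.3 | 1.327 | 25.9% | 1.643 | 37.1% |
| 0.4 | 1.769 | 41.6% | 2.191 | 58.4% |
| 0.5 | 2.211 | 58.9% | 2.739 | 77.5% |

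A normal approximation gives 19.5% to 78.2% at 60 per arm, so the choice of method hardly matters. The number of scars scored matters more. With 54 per arm, the normal approximation gives 18.0% at 0.2 SD and 73.8% at 0.5 SD.

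At 0.2-0.3 SD a false positive is still less likely than not in both cases. It passes one half at 0.4 SD with 60 per arm, and between 0.4 and 0.5 SD with 48 vs 33. A masked rating removes the systematic shift and returns the rate to 5%.

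**The case against.** The strongest reply is that the plan is silent here, and silence does not prove a defect. A reader might infer that unblinded site investigators score the scar, because it is assessed at visits. The documents do not support that. Data collection and follow-up also places planimetry at each visit, yet Randomization and Blinding assigns planimetry to a blinded central reader. In this document, then, a visit reference gives timing and does not identify the rater. This part of the objection stands.

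Wound parameters could also be meant broadly enough to include the scar of the target ulcer, and the photographs were taken partly for independent assessment. Both are possible. However, the only example of a wound parameter is planimetry, item 7 lists the scar separately from area and closure, and nothing ties the photographs to the scale. These points weaken an inference from omission but do not establish masking.

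The percentages depend wholly on an assumed shift. The documents give no SD and no sign that any rater favoured a product. That is correct, so the figures show how sensitive the test is to such a shift and do not estimate bias in this trial.

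Finally, photographs of healed ulcers may be missing. Before the Study completion section, the plan says that no further procedures take place at a visit where the ulcer has fully re-epithelialised, and it describes photography for ulcers that have not healed. Study completion treats patients whose ulcers close early as finished at closure. Against this, wound area by photograph-based planimetry is scheduled through day 35. The tension is real and has to be settled for a photographic reading to work.

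**Conclusion.** The point holds as a gap in protection against assessor bias. Scar quality is a judgement-based between-arm outcome in an open-label trial, it is not named among the masked assessments, and neither its rater nor any masking is stated. It does not hold as a finding that unblinded investigators produced the scores, nor as evidence that a biased result is likely.

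The size is conditional. If the rating was unmasked and shifted by 0.2-0.5 SD, the 5% error rate becomes about 14-59% with 48 vs 33 closed ulcers, or about 19-78% with 60 per arm. This rests on the assumed shift, on no true difference, on a t-test, and on the assumed number of scars scored. It is a minor point, because it concerns the last of the listed secondary outcomes.

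**What to change.** In Randomization and Blinding and in secondary outcome 7, add a scar rating by the existing blinded central reader. It should use the masked week-5 photographs, be read in random order, and cover only items that a photograph shows. Rest any between-arm significance claim about scars on this reading.

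State who scores the bedside Vancouver Scar Scale and whether that rater is masked. If not, report the bedside scale as descriptive and unblinded, with no significance claim. If the rating was masked, say how; that restriction is then unnecessary. Because the text describes conduct in the past tense, the wording must report what was actually done. A masked reading can still be made from stored photographs.

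Two sets of passages must be reconciled at the same time: completion at closure with the day-35 assessment, so that healed ulcers have a photograph, and the scar timing in item 7 (week 5) with that in Data collection and follow-up (every visit). The set of patients scored should also be stated.

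The cost is one more field for the central reader, plus protocol wording. The downside is that items needing touch cannot be scored from a photograph, so the masked reading covers only part of the scale.

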If the study ulcer was found to be 100% re-epithelialized during the visit, no further study procedures were conducted at that time. The patient was then scheduled for a follow-up visit after one week to confirm the healing. If complete healing was not observed, an assessment was performed to check for signs of clinical infection. If an infection was diagnosed, treatment with topical antimicrobials (betadine, chlorhexidine) or oral antibiotics was allowed, but the use of topical antibiotics (erythromycin, polymyxin, mupirocin) was prohibited.

Following the infection assessment, the ulcer was cleaned, photographed, and debrided at the investigator's discretion to ensure a clean, granulating ulcer base with minimal adherent slough. The SOC was then reapplied, and the patient was instructed to keep the bandaging dry. The patient was also advised to contact or visit the study site if the bandage became soiled or was removed. Topical antibiotics specifically on the wound were prohibited.

Systemic antibiotics were permitted when clinically needed.

Study completion

Patients completed the study four weeks after their first treatment visit. However, if a patient's study ulcer closed before the four-week mark, they were considered to have completed the study at that time. Complete healing of the study ulcer was defined as 100% re-epithelialization with no drainage. Throughout the treatment period, patients had the right to refuse participation or withdraw from the study at any time without prejudice. If a patient chose to withdraw from the study, their last recorded wound measurement was carried forward and used to calculate the change in wound size and their final outcome.

Outcome Measures

Primary Outcome:

1. Proportion of participants achieving wound size reduction at 4 weeks, measured using digital planimetry. Wound area was monitored at visits on days 7, 14, 21, 28 (intervention period) and 35 (follow-up period)

Secondary Outcomes:

1. Histological assessment of vascular incursion and wound biology was performed using punch biopsies (2mm diameter) obtained from the wound edge on day 5 post-treatment initiation. Histological parameters were evaluated using standardized scoring scales, including:

- a. vascular infiltration assessed on a 0-3 scale based on vessel count per high-power field,
- b. neo-epithelialization measured on a 0-3 scale based on epithelial migration distance from the wound edge,

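### The position of the histology punches is left open and the biopsy operator is not listed as blinded, so blinded slide reading does not guard against an arm-dependent choice of site

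*Combined protocol and SAP*

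**What the plan says.** **Site and timing.** Secondary outcome 1 under Outcome Measures describes punch biopsies "obtained from the wound edge on day 5 post-treatment initiation". The histopathology paragraph that follows gives the fuller procedure: "a 2 mm punch biopsy was obtained from the wound edge extending into the wound bed", taken "before application and on the fifth day after the application of either HPTC or dHCAM". The title of Table 1 reads "Histological parameters evaluated in the ulcer bed at baseline and on day five of application".

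**Use.** The two biopsies are set against each other: "Vascularity assessment was done using biopsy on day zero of application to be compared with day five". Six parameters are evaluated. Five are scored 0 to 3 and one, capillary density, is a count per mm².

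**Blinding.** Randomization and Blinding states that "participants and investigators could not be blinded to treatment allocation". It then lists the blinded assessors: a central planimetry reader, and those for whom "histological analysis and quality of life measurements were blinded to treatment assignment". The histopathology paragraph adds that "All histological assessments were performed by two independent pathologists blinded to treatment allocation", with Cohen's kappa for agreement.

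**What is not stated.** No section says who takes the biopsy, where around the edge it is taken, or how far the day-5 punch must lie from the day-0 punch.

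**The concern.** An ulcer does not heal evenly, and one small core per visit stands for the whole wound. Someone who knows the arm and sees the wound could, without intending to, sample a healthier-looking spot more often in one arm. Blinding the readers acts only after that choice. Kappa measures whether two readers agree on the same slide and says nothing about where the tissue came from.

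A second issue concerns the day-0 to day-5 change. The day-0 punch is itself an injury to the ulcer, and nothing keeps the day-5 punch away from it. If the two lie close together, the change may partly reflect repair of the first punch.

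Histology is the first-listed secondary outcome. The Introduction gives it particular emphasis and states a wish to confirm that HPTC is superior through greater cellular activity. In an open-label trial with a declared expected direction, the choice of tissue deserves the same protection as its reading.

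**Working it through.** The plan gives no figure for this point, so there is none to reproduce. The check has three parts.

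**1. Which steps are protected**

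| Step | Who | Blinded according to the plan? |
|---|---|---|
| Choice of punch site | Not stated | Not listed; investigators are unblinded |
| Slide scoring | Two pathologists | Yes |
| Planimetry | Central reader | Yes |

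The first row is the gap.

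**2. Room for choice**

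Eligible ulcers measure 5 to 20 cm² (Inclusion criteria). Assume a circular outline. The edge length is 2√(πA):
- A = 5 cm²: 7.9 cm, or 79 mm / 2 mm ≈ 40 adjacent punch sites.
- A = 20 cm²: 15.9 cm, or 159 mm / 2 mm ≈ 79 sites.

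A 2 mm core has area π × 0.1² = 0.0314 cm², which is 0.63% to 0.16% of the ulcer. There is ample room to choose. Equally, nothing suggests that adjacent punches would be common.

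**3. What selection in one arm could do**

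Inputs from the plan:
- 60 per arm and 10% dropout (Sample Size Calculation), so 60 × 0.9 = 54 per arm.
- Two-sided 5% level and a t-test (Statistical Analysis).

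Assumptions, which the plan does not give:
- no true difference;
- a continuous normal outcome with total SD 1;
- a share w of the variance lies within the ulcer;
- in a fraction f of one arm only, the operator takes the better-looking of two spots;
- appearance correlates r with the histology value.

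The expected maximum of two standard normal values is 1/√π = 0.564, so the bias in SD units is

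d = f × r × √w × 0.564.

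For w = 0.5, r = 1 and f = 1, d = 0.707 × 0.564 = 0.40. The standard error of the difference is √(2/54) = 0.192. Simulated rejection rates at w = 0.5 (40,000 replicates per cell) are:

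| Share of one arm selected | Bias, r = 1 | Rejection, r = 1 | Bias, r = 0.5 | Rejection, r = 0.5 |
|---|---|---|---|---|
| 0% | 0 | 5% | 0 | 5% |
| 25% | 0.10 SD | 8% | 0.05 SD | 6% |
| 50% | 0.20 SD | 18% | 0.10 SD | 8% |
| 100% | 0.40 SD | 57% | 0.20 SD | 18% |

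The cells shown as 18% come out at 18% to 19% in shorter runs. At r = 0.3 the three non-zero rows fall to about 5%, 6% and 9.5%.

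Varying w from 0.25 to 0.75, rejection for f = 25%, 50% and 100% is:
- r = 1: 7% to 10%, 11% to 25%, and 32% to 77%.
- r = 0.5: 5% to 6%, 7% to 10%, and 11% to 25%.

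**The case against.** Several objections are sound and limit the point.

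- **The operator.** A reader might infer that an unblinded investigator chose the sites. The procedure is in the passive voice and names nobody. The inference is reasonable, because no blinded operator is listed, but it remains an inference.
- **Blinded reading has value.** It protects against biased scoring, a main risk with four-level scales. Only the choice of site is left open.
- **The day-0 punch.** A reader might infer that repair around it biases the comparison of products. Both arms have that punch. If proximity is similar in the two arms, it distorts the within-arm change and may dilute a product difference; it biases the between-arm contrast only if proximity differs by arm. The documents do not report how the tissue beside the punch looks at day 5.
- **Direction.** A reader might infer that all six parameters would shift towards one product. That is not shown. A spot that granulates well need not show more epithelial migration, and a higher inflammation score means more severe inflammation.
- **Site wording.** The three descriptions of the site are largely compatible: a short form, the full procedure, and a loose table title. Aligning them is editorial.
- **The simulation.** The r = 1 column is a ceiling, the selection is wholly one-sided, and five of the six outcomes are four-level scores rather than continuous values.

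The document is also in the past tense, so a position rule may come too late for most biopsies. What survives is the gap itself: site choice is neither fixed by rule nor shown to be blinded, and no later step can repair it.

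**Conclusion.** The concern holds, for the secondary histology outcomes only. The plan leaves the position and separation of the two punches open and does not show that the person choosing them was unaware of the arm. An arm-dependent choice could therefore bias the between-arm histology comparison despite blinded reading.

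The possible size ranges from almost nothing to large. At w = 0.5, selection in half of one arm raises a nominal 5% error rate to about 8% (correlation 0.5) or 18% (perfect correlation); selection in every patient of one arm raises it to about 18% or 57%. These figures rest on an assumed within-ulcer variance share, one-sided selection and a normal outcome. They show vulnerability. The documents contain no evidence that selection took place, and they do not support calling the histology results biased.

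**What to change.** **Biopsies not yet taken.** Set both positions by a rule fixed before the allocation envelope is opened, and record the position used. Two options:
- opposite clock positions on the baseline photograph, for example day 0 at 12 o'clock and day 5 at 6 o'clock;
- a position drawn with the randomisation list, with the day-5 site placed opposite the day-0 site.

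Name in advance an alternate for an unusable position, such as the next clock hour. Opposite positions also separate the punches: on a circular ulcer the distance is the diameter, 2√(A/π), about 2.5 cm at 5 cm² and 5.0 cm at 20 cm² at baseline. Use one description of the site in secondary outcome 1, the biopsy procedure and the title of Table 1.

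**Biopsies already taken.** State who took them and whether they knew the arm. Where photographs allow, report the punch positions by arm and how many day-5 punches adjoined the day-0 punch. The plan says that photographs were taken, but not that they show the punch site, so this may not be recoverable for every patient. Where it is not, present the histology comparison as open to site-selection bias.

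**Cost.** Prospectively, a sentence in the procedure and a mark on a photograph, with no extra biopsy or reader; the small downside is that a position will occasionally be unusable. Retrospectively, a review of existing photographs and a short statement in the report.
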